## **6. Written Informed Consent**

Written Informed Consent must be obtained for all patients who are potential study candidates.

Patients who meet pre-op inclusion/exclusion entry criteria will be invited to participate, and asked to sign the study-specific, Institutional Review Board (IRB)-approved Informed Consent form before any study-specific tests or procedures are performed. Study personnel should explain that even if a patient agrees to participate in the study and signs an informed consent form, the Investigator may determine that the patient is not a suitable candidate for the study.

A Screening/Enrollment Log will be maintained to document select information about candidates who fail to meet the entry criteria.

## **7. Study Procedures and Enrollment**

### ***7.1. Duration of Subject Participation***

Subjects enrolled in the trial will participate for approximately 30 (+/- 7) days.

### ***7.2. Enrollment***

At the completion of the procedure, subjects that meet all the intra-operative eligibility criteria will be randomized 1:1 to use either the Cardiva Mid-Bore VVCS or manual compression for access site hemostasis of all venotomies. Randomization will be stratified by 3 vs. 4 access sites. Once a subject has been randomized, he or she is considered enrolled into the study. See Section 5.2 Withdrawal of Subjects.

### 7.3. Visit Schedule

The following outlines the required study assessments.

**Table 3. Study Event Schedule**

	≤ 45 days before Procedure	At time of Index Procedure	Post-Procedure/ Hospital Discharge	1-Month (30 days) ± 7 days
Demographics/ Medical History	X			
Groin assessment		X	X	X
Complaints of pain/nerve injury in lower extremities	X		X	X
Laboratory Tests*:	X			
Pre-op Inclusion / Exclusion Criteria Assessment	X			
Informed Consent	X			
Intra-procedural Exclusion Criteria Assessment		X		
Randomization and Intent to Treat / Enrollment		X		
Study Endpoint Data Collection:**				
TTCE determination		X		
TTH determination		X		
TTA determination			X	
TPPT determination			X	
TTDE determination			X	
TTD determination			X	
Device Success		X		
Procedure Success				X
Anti-platelet / anti-coagulant regimen		X	X	
Pain/anxiety medication regimen			X	
Patient Experience Survey			X	
Adverse Events		X	X	X
Ultrasound Exam (50 subjects)				X

\*For subjects on warfarin, document most recent INR prior to the procedure

\*\*The following study endpoints will require collection of specific clock times, but results will be calculated within the database:

- TTCE: Time to Closure Eligibility (by patient)
- TTH: Time to Hemostasis (by access site)
- TTA: Time to Ambulation (by patient)
- TPPT: Total Post-procedure Time (by patient)
- TTDE: Time to Discharge Eligibility (by patient)

- TTD: Time to Discharge (by patient)

## **7.4. Study Procedures**

### **7.4.1. Pre-Operative**

Prior to the subject's scheduled procedure, obtain a medical history and record the subject's demographic data (age, race, ethnicity, and gender) and baseline information (height, weight, BMI). Review the Pre-operative Inclusion and Exclusion criteria within 45 days prior to the planned procedure date, including collection of the following routine blood tests:

- serum creatinine
- platelet count
- hemoglobin and hematocrit

Review of the subject's medical history and risk factors will be documented. The subject will be asked about any pre-existing lower extremity nerve complaints in both lower limbs (i.e., symptoms, severity). Peri-procedural medications that are taken within 24 hours of the procedure that may affect bleeding (e.g., anti-platelet, anti-coagulant, anti-thrombotic agents, etc.) will be documented.

Document the most recent INR for subjects on warfarin.

### **7.4.2. Intra-Operative – Data Collection for All Subjects**

For consented subjects that continue to meet the Pre-operative Eligibility Criteria, record the following data regarding their procedure:

- procedure type: A-Fib, Other
  - If A-Fib, record: paroxysmal, persistent, and chronic / permanent, other
- ablation modality (e.g., RF, Cryo)
- **P0 TIME:** time of first index procedure sheath insertion
- number and location of access site locations (3 or 4)
- techniques used to gain venous access, if any (e.g., ultrasound, micropuncture)
- procedural anti-coagulation administered
- final procedural ACT time and value
- protamine administration, dose and time (if given)
- time of extubation

### **7.4.3. Intra-Operative – Access Site Requirements**

The following procedural requirements apply to all subjects enrolled in this study:

- A maximum of 2 femoral venous access sites are allowed per limb.

- All access sites must have procedural sheaths with a minimum of a 6 Fr and a maximum of a 12Fr sheath inner diameter at the end of the case.
- Sheaths larger than 9 Fr must be placed in separate limbs (e.g., cannot place two 10 Fr sheaths in one limb).
- Refer to the Cardiva Mid-Bore VVCS IFU for specific instructions on device use.

#### 7.4.4. Intra-Operative Randomization

At the end of the catheter-based procedure, with the procedural sheaths in place and under fluoroscopic visualization, an injection of contrast will be made to assess sheath placement and the anatomy of all venous access sites to verify the intra-operative eligibility criteria prior to randomization. These images should be saved and printed/stored with the subject's study records for monitoring purposes.

- Each venous access site must meet all intra-procedural access site-specific criteria for the subject to be eligible.

Once it has been determined that the subject does not meet any of the general intra-operative exclusion criteria, and that none of the venous access sites meet the specific access site exclusion criteria (i.e., all venous access sites must meet all study criteria for the subject to be eligible), then the subject is eligible for randomization.

- Once randomized, every access site will be closed according to the treatment assignment (i.e., either VVCS or manual compression).
- Study data will be captured for each access site, according to the instructions below.
- ***NOTE: Any subject that is randomized is considered to be enrolled, and all peri-procedural study data must be collected under the Intent to Treat principle regardless of deviations from the assigned treatment. For this reason, it is imperative that randomization is not performed until the case is complete and final eligibility criteria are confirmed.***
- ***If the subject is randomized to Mid-Bore VVCS and it is subsequently discovered that one or more of the access sites is not able to be closed (e.g., complication) apply manual compression to the affected access sites and close all eligible access sites using Mid-Bore VVCS. All study data will still be collected for each access site. See Section 4.2 Withdrawal of Subjects.***

At each investigational site, variable block randomizations will be performed separately by number of venotomy sites via EDC access at the conclusion of the index procedure, while the patient is on the table. Randomization will be stratified by 3 vs. 4 access sites, and there will be a 1:1 randomization ratio for Cardiva Mid-Bore VVCS vs. manual compression for access site closure. Refer to the Manual of Operations for instructions on how to randomize a subject.

#### 7.4.5. Access Site Closure Instructions

The following process will be used to collect procedural data for each of the treatment arms:

**Mid-Bore VVCS Treatment Arm Guidelines**

If the subject is randomized to receive the Mid-Bore VVCS, the device should be deployed according to procedure in the Instructions for Use (IFU) provided in **Attachment 3**. If protamine is administered, the Investigator may proceed immediately with sheath exchanges and VVCS deployment without re-checking the ACT to obtain a target value.

Document device information:

- Device Lot #
- Device Success evaluation
- Document any complications or device performance issues on the Device Performance eCRF; refer to the Manual of Operations for device return instructions in the case of any device performance issues.

**Manual Compression Guidelines:**

If the subject is randomized to receive manual compression, it should be performed according to the institution's standard practice. If protamine is administered, the Investigator should follow institutional practice guidelines for re-checking ACT levels and/or waiting a specified time or for a target ACT value prior to removal of sheaths and application of manual compression.

**Documenting Access Site Hemostasis in Both Treatment Arms:**

While performing the procedure, record the following information:

- **P1 TIME:** time of removal of final index procedure device/catheter
- For each access site, record:
  - Access site location, e.g., right/left leg and relative location with respect to 2nd access site, if applicable e.g. proximal/distal, medial/lateral, etc.
  - Final introducer sheath size (inner diameter and length) at time of closure (i.e. after final sheath exchanges)
  - **TX.1 TIME:** time of removal for Mid-Bore VVCS device (treatment arm) or for removal of sheath (control arm)
  - **TX.2 TIME:** time venous hemostasis is achieved
  - Confirm that venous hemostasis is maintained and confirmed at 5 minutes after recorded hemostasis time (TX.2).
  - Document any light manual compression applied for tissue tract ooze.

Note: *For VVCS arm, formation of a hematoma post-sheath removal may indicate a back-wall or secondary venous or arterial puncture. If this situation is suspected, the VVCS should be removed and the subject should be converted to manual compression at that location. Additional access*

 source worksheets and clock/timers will be provided and required by Sponsor

*sites may still be closed with Mid-Bore VVCS, as appropriate.*

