**Figure 1: Cardiva Mid-Bore VVCS with Disc Deployed**

To use the Cardiva VVCS, the catheter is inserted into the femoral vein through the previously placed introducer sheath. After insertion, the distal tip of the catheter is deployed, opening and expanding a low-profile Nitinol (NiTi) disc within the lumen of the femoral vein. The introducer sheath is then removed from the vessel over the catheter and the low-profile disc is placed against the inner wall, locating the vessel wall and temporarily sealing the venotomy. The position of the device disc against the vessel wall locates the collagen patch in the tissue tract immediately adjacent to the venotomy site (extravascular) and its location is verified using fluoroscopy prior to release. The clip is placed on the device shaft at the surface of the skin to hold the device in place during fluoroscopy.

Note, the principle of operation and the steps described below are identical to that of the previously approved device. Refer to the Instructions For Use document in **Attachment 3**.

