**(Per patient analysis).**

*TTCE will be reported in minutes (hh:mm).*

- **Time to hemostasis (TTH)**, defined as elapsed time between removal of the Mid-Bore VVCS device (treatment arm) or removal of the sheath (control arm), and first observed and confirmed venous hemostasis, for each access site. **(Per-access site analysis)**

*TTH will be reported in minutes (mm): seconds (ss).*

**Total Post-Procedure Time (TPPT):** defined as elapsed time between removal of the last procedural device/catheter for the index procedure and when subject is able to successfully ambulate. **(Per-patient analysis)**

*TPPT will be reported in hour (hh): minutes (mm).*

**Procedure Success**, defined as attainment of final hemostasis at all venous access sites and freedom from major venous access site closure-related complications through 30 days  

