**Table 4: Study-required Data Collection and Endpoint Calculations**

Time Point	Reported Units	Procedure Step	TTCE	TTH	TTA	TTDE	TTD	TPPT
P0	hh:mm	Index Procedure: First procedure sheath inserted						
P1	hh:mm	Index Procedure: Final Device/Catheter removed from sheath						
-	-	Final Sheath Exchange, as applicable						
T1.1	hh:mm:ss	Access Site 1 - start hemostasis*			T1.2-T1.1			P2-P1
T1.2		Access Site 1 - confirmed hemostasis						
T2.1		Access Site 2 - start hemostasis*			T2.2-T2.1			
T2.2		Access Site 2 - confirmed hemostasis						
T3.1		Access Site 3 - start hemostasis*			T3.2-T3.1			
T3.2		Access Site 3 - confirmed hemostasis						
T4.1		Access Site 4 - as applicable start hemostasis*			T4.2-T4.1	P2-TX.1	P3-TX.1	
T4.2		Access Site 4 - confirmed hemostasis						
P2	hh:mm	Ambulation					P4-TX.1	
P3		Discharge Eligibility - per medical team						
P4		Discharge						
		*Where "start hemostasis" is: Treatment: VVCS removal Control: Sheath removal				Where "X" is final access site for the patient, shown here aligned with access site 4 for simplicity.		

hh: hours; mm: minutes; ss: seconds

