#### 9.2.2.2 Secondary Effectiveness Endpoints Analyses

Secondary effectiveness endpoints include total post procedure time (TPPT), time to discharge eligibility (TTDE), and time to discharge (TTD).

TTH will be compared between the two study arms by the bootstrap method with patient as the re-sampling unit as opposed to access site, as within patient TTH times may be correlated. Otherwise the analysis will be similar to those for the primary safety analysis described in 8.2.3, and the proposed TTH non-inferiority margin will be 5 minutes for VVCS as compared to manual compression.

Lastly, time to closure eligibility (TTCE), procedure success, and proportions of device success (VVCS only, by access site) will be descriptively summarized without hypothesis testing.

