**Fig. 6 – Insert device into hub of introducer sheath**

**Fig. 7 – Insert device half way of the Lock**

**Fig. 8 – Pull back on Black Actuator Tip to deploy the MID-BORE VVCS Disc**

**Fig. 9 – Grasp hub of sheath and remove over catheter**

- Deploy the Disc by holding the Silver Handle and pulling back the Black Actuator until it locks in place as shown in **Figure 8**.

**CAUTION:** Do **not** continue to pull on the Black Actuator once it is locked in place as this may damage the device.

**NOTE:** When the Disc is properly deployed, the Green Segment will become visible distal to the Black Actuator. If the catheter is not properly locked in place, the Black Actuator will slide back to its original position and the Green Segment will disappear indicating that the Disc is not properly deployed. In this case repeat the step for deploying the Disc by pulling the Black Actuator more firmly until it locks in place.

10. Gently remove sheath, without applying any compression at the access site or holding the MID-BORE VVCS Catheter, as shown in **Figure 9**. As the sheath slides over the MID-BORE VVCS Catheter, grasp the Catheter proximal to the LOCK as it exits the distal end of the introducer sheath. Continue sliding the sheath over the MID-BORE VVCS Catheter and discard sheath.

**CAUTION:** Compressing the access site during sheath removal may not allow the Disc to track back to the venotomy and may cause Disc deformation. This may lead to inability to achieve temporary hemostasis.

11. Apply gentle tension on the Black Actuator until temporary hemostasis is achieved. Note whether any portion of the White Marker Stripe, which is located near the distal aspect of the Black Sleeve, is visible above the skin. If it is, then the length of the tissue tract is less than 2.5 cm, indicating the tissue tract may not be long enough for the Collagen Patch.

**WARNING:** If any portion of the White Marker Stripe is showing DO NOT RELEASE the Collagen Patch as this may increase the risk of infection.

**NOTE:** If any portion of the White Marker Stripe is showing and the collagen patch is not to be deployed, the MID-BORE VVCS Catheter should be removed by collapsing the Disc and manual compression should be applied per institutional protocol.

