14. AFTER 15-30 seconds of patch swell time and PRIOR TO collapsing the Disk, remove the Clip. Rest the palm of the hand on the patient and grasp the green tube between the thumb and the index finger as shown in **Figure 15**. Push the green tube in the proximal direction approximately 1.5 cm while gently pulling back on the MID-BORE VVCS Catheter to maintain Disk position against vessel wall. The green tube may be slid back and forth 2-3 times in order to assure release of the Collagen patch from device. Upon completion of this step, leave the green tube in the forward position. Apply gentle compression at the site and collapse the Disc by pressing on the Black Actuator Tip as shown in **Figure 16**. Apply gentle manual compression at the site as the MID-BORE VVCS Catheter is removed. Continue to apply manual compression.

15. Observe for complete hemostasis. Manual compression can be used to decrease or stop any tract ooze until full hemostasis is achieved.

**NOTE:** Prior to the MID-BORE VVCS Catheter removal confirm that the Disc is completely collapsed by verifying that the Green Segment on the handle is no longer visible. Care should be taken not to compress too firmly over the VVCS catheter during the removal step of the device so that the catheter can be easily removed and without displacement of Collagen Patch. Note: The implanted Collagen Patch should not be affected by Magnetic Resonance Imaging (MRI).

16. Apply sterile dressing to site per institution protocol. Maintain bed rest and periodically check site until patient is ready to ambulate.

17. Complete information on Patient Implant Card and provide to the patient.

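### Time to hemostasis starts at device removal for VVCS but at sheath removal for control, so on a common sheath-removal clock the 5-minute non-inferiority margin is wider than 5 minutes by an interval that the protocol does not list for recording

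*Combined protocol and SAP*

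**What the plan says.** Section 8.2 gives TTH, per access site, as "defined as elapsed time between removal of the Mid-Bore VVCS device (treatment arm) or removal of the sheath (control arm), and first observed" hemostasis that is then confirmed. Section 7.4.5 records the start, TX.1, as the "time of removal for Mid-Bore VVCS device (treatment arm) or for removal of sheath (control arm". The note under Table 4 repeats the rule: "Treatment: VVCS removal Control: Sheath removal". The stop, TX.2, is the time hemostasis is achieved.

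On the order of events with the device, Section 2 says: "The introducer sheath is then removed from the vessel over the catheter and the low-profile disc is placed against the inner wall". The IFU (Attachment 3) places this at step 10: "Continue sliding the sheath over the MID-BORE VVCS Catheter and discard sheath". Step 11 is tension until temporary hemostasis, step 12 the clip and the fluoroscopic check, and step 13 the release and retraction of the sleeve. Step 14 begins: "AFTER 15-30 seconds of patch swell time and PRIOR TO collapsing the Disk, remove the Clip". The green tube is then worked, the disc is collapsed and the catheter is withdrawn. TX.1 for a VVCS site is read at that withdrawal.

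Section 9.2.2.2 compares TTH between arms by the "bootstrap method with patient as the re-sampling unit as opposed to access site", otherwise following the primary safety analysis, and states that "the proposed TTH non-inferiority margin will be 5 minutes for VVCS as compared to manual compression". In the safety analysis the upper limit of a two-sided 95% interval is set against the margin.

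The clock times listed in Sections 7.4.2, 7.4.5, 7.4.6 and Table 4 are P0, P1, TX.1, TX.2, P2, P3 and P4.

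**The concern.** Sheath removal happens at every site in both arms. Control TTH starts there. VVCS TTH starts one deployment cycle later. Call the gap d. It cannot be negative, so leaving it out always favours VVCS.

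The gap can include bleeding control. Step 11 applies tension until temporary hemostasis is reached, so hemostasis is not taken for granted once the sheath is out, and the IFU warns that it may fail if venotomies lie too close together. Section 7.4.5 foresees a hematoma after sheath removal, with the device then taken out and the site converted to manual compression. At such a site the time lost before the device comes out is not in TTH.

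No other endpoint supplies the missing interval for each site. TTCE ends when the first device comes out, so it covers d for the first site only. TPPT includes all closure time, but it is one figure per patient in hours and minutes and runs on to ambulation.

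At stake is what a finding of TTH non-inferiority within 5 minutes would mean. Read as time from sheath removal to hemostasis, it would claim more than the test shows.

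**Working it through.** **The plan's own figures.** The plan states no power for TTH. Its stated powers for the primary endpoints reproduce. For TTA, SE = 5.4 × √(2/102) = 0.756 h. Then Φ(2.2/0.756 − 1.96) = 0.829 against the stated 0.83, and Φ(2.9/0.756 − 1.96) = 0.970 against 0.97. For safety, exact enumeration of the Newcombe upper limit with 204 limbs per arm and 2% in each gives 0.877 against 0.88.

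**Inputs for TTH.**
- Margin: 5 min (Section 9.2.2.2).
- 102 patients per arm (Section 9.3).
- SDs 5.4 min (device) and 12.4 min (manual compression), means 4.8 and 21.4 min (Table 2, RESPECT). RESPECT was arterial, so using these values here is an assumption.
- One TTH value per patient, a normal approximation and a constant d: assumptions.
- d: only the swell time is documented, 15-30 s = 0.25-0.5 min (IFU step 14). Values of 1 and 2 min are assumed.

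**Effective margin.** Let Δ be the true VVCS minus control difference from sheath removal. The planned test sees Δ − d and compares it with 5. On the sheath-removal clock the margin is therefore 5 + d.

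**Error at the margin.** SE = √[(5.4² + 12.4²)/102] = √(182.92/102) = 1.34 min, and the 95% half-width is 1.96 × 1.34 = 2.62 min. At Δ = 5 the chance of declaring non-inferiority is Φ(d/SE − 1.96):

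| d (min) | Source | Margin on sheath-removal clock (min) | One-sided error (nominal 0.025) |
|---|---|---|---|
| 0.25 | swell time, lower | 5.25 | 0.038 |
| 0.5 | swell time, upper | 5.5 | 0.056 |
| 1 | assumed | 6 | 0.113 |
| 2 | assumed | 7 | 0.320 |

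A smaller SE makes the inflation larger. With an SD of 5.4 min in both arms (SE 0.756 min) the four errors are 0.052, 0.097, 0.262 and 0.753.

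**What d would change the conclusion.**
- RESPECT difference: 4.8 − 21.4 = −16.6 min. Upper limit −16.6 + 2.62 = −13.98 min. d would have to reach 5 + 13.98 = 18.98, about 19 min.
- Observed difference of zero: upper limit 2.62 min. d of 5 − 2.62 = 2.38, about 2.4 min, would be enough (3.5 min with both SDs at 5.4).

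**What the listed times allow.** VVCS sheath removal falls between P1 and TX.1, so P1 to TX.2 is an upper bound on the time from sheath removal to hemostasis. The bound is loose. P1 is recorded only to the minute and precedes any sheath exchange, and for later sites the interval spans the earlier closures. For a later site in the same limb, the previous site's TX.2 is a tighter anchor if the IFU's proximal-then-distal order was followed. An exact value cannot be rebuilt.

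**The case against.** The start rule has a rationale. It starts both clocks when the last closure hardware leaves the vein, and it is stated consistently throughout. While the device is in place the disc is meant to seal the venotomy temporarily, so a sheath-removal clock would count time when bleeding is already held. Compression after the catheter is withdrawn (IFU steps 14 and 15) does count in VVCS TTH, as does compression after a device is removed at a converted site. TTH is secondary. Under Section 3, trial success rests on TTA and primary safety, and the proposed indication claims ambulation and discharge eligibility, not hemostasis time. The only TTH data in the documents show a gap too large for a few minutes to matter.

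Most of this stands, and it rules out several stronger readings that a reader might infer:

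- *That the definition is an error, or that sheath removal must be the main clock.* The definition is explicit, and given the disc's role the choice between clocks is debatable.
- *That the VVCS clock starts only when closure is finished.* Compression after device removal is inside the measured interval.
- *That the problem is beyond repair once data are collected.* P1 to TX.2 allows a conservative, if loose, sensitivity test.
- *That sheath removal is recorded nowhere.* The source worksheets and the Manual of Operations are not among the documents, so its absence is shown only for the protocol's lists.
- *That the current rule is RESPECT's.* The documents do not state RESPECT's TTH start event.

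The objection does not remove the asymmetry. RESPECT's difference is arterial and may not carry over. Because the plan sets a non-inferiority margin for TTH, a small or zero difference has to be considered, and there a few minutes would matter.

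**Conclusion.** The point holds as a limited one. The TTH test compares unequal intervals, the inequality always favours VVCS, and the 5-minute margin acts as 5 + d minutes from sheath removal. The documented part of d, 15-30 s, is 5-10% of the margin (0.25/5 to 0.5/5) and by itself raises the error at the margin from 0.025 to 0.038-0.056. Any larger figure depends on an assumed d. All the error figures rest on RESPECT's arterial SDs and one value per patient.

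Whether the conclusion would change depends on d and on the venous TTH difference, and the documents give neither. The trial's success criteria are not affected. The same arm-specific start is used for TTA, TTDE and TTD, but those run over hours and this point makes no claim about them. The change below is worth making because it is cheap and an exact reading has to be taken during the procedure.

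**What to change.** 1. Add sheath-removal time (hh:mm:ss) for each VVCS access site to the list in Section 7.4.5 and to Table 4. In control it already equals TX.1.
2. Keep the current TTH definition as the main TTH analysis.
3. Pre-specify in Section 9.2.2.2 a sensitivity analysis of TTH from sheath removal to TX.2 in both arms, with the same patient-level bootstrap and the same 5-minute margin.
4. State the start event with any claim of TTH non-inferiority.

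If the worksheets already capture VVCS sheath removal, only the last three steps and a matching entry in the protocol are needed.

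The cost is one clock reading and one eCRF field per VVCS site, on timers the sponsor already requires, and one more bootstrap run. VVCS TTH will look slightly longer in the sensitivity analysis.
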